Aim 1: Feasibility will be assessed through examination of participant recruitment, retention and engagement. Specifically, we will look at the number of participants who refuse to participate in the pilot at the time of recruitment and the reason they declined participation. Secondary impacts of interest include: medication adherence as measured by the four-item MA Questionnaire (MAQ) and change in systolic and diastolic blood pressure at 3 months.

Aim 2: To test the acceptability of a 3-month SMS-based intervention in adults with uncontrolled hypertension. One cohort of 24 participants will be recruited for the SMS intervention. Acceptability will be assessed using the systems usability scale (a validated questionnaire that measures usability reliably in small samples)¹⁸ and eliciting free comments after the survey.

At the end of this pilot project, we will have preliminary data essential for a future formal efficacy trial, to be proposed in a subsequent application to the AHRQ.

Our **first hypothesis** is that over 50% of contacted patients will respond to SMS messages and over 50% will check HBPM. This estimate is based on previous study by Bobrow and

colleagues in a similar patient population.³ Our **second hypothesis** will be that > 75% will be satisfied with the service (OK or above on the usability survey).⁹

Methods and Measures

Design

A randomized control trial of 24 non-adherent participants will be monitored and followed for 3 months; An ambulatory BP arm device will be provided to all participants with printed instructions in English or Spanish (from the American Heart Association) on how to measure BP at home (HBPM). Patients will be instructed on checking their BP at least twice a week.^{14,19} Text messages will be generated by Twilio platform, keeping a record of participants contacted, sent and received texts. Participants in the control arm will receive standard of care education for controlling high blood pressure in clinic by their healthcare providers. They will be followed to monitor any changes in their BP throughout the duration of the study.

Study team members will identify patients with uncontrolled hypertension during clinic visits. Study team members will approach patients 18 years or older who have uncontrolled HTN (SBP>130 or DBP >80) and have 2 or more BP medication(s) on their medication list.

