recommendations by HTN guidelines, which designate a hypertensive urgency to be 180/110 mm Hg or higher and hypotension 90/60 or lower.²

Patients who no show to the follow up visits will be telephoned to assess adherence barriers. The study team member will create a telephone encounter in the electronic health record to document their discussion and route it to the patient's PCP. Patients who refuse participation in the study will be asked for the reason and their responses will be recorded to determine any barriers to participation. Study team members will attempt to contact patients who miss follow up visits every week up to 3 times, if after the 3rd time the patient is still not able to be reached, the patient will be lost to follow up.

Setting

The study team will recruit patients who fall within the eligibility criteria from Wake Forest Baptist Medical Center.

Subjects selection criteria

Eligibility and recruitment

Inclusion criteria

Patients 18 years and older who have SBP>130 or DBP >80 during an office visit encounter in the past 6 months and have BP medication(s) on their medication list.

- Own a phone with SMS capability
- Non-adherent-MAQ score of 1 to 4
- Vulnerable population (Black, Hispanic or education level < or equal high school (as an indicator of low SES)

Exclusion Criteria

- End-stage renal disease (on hemodialysis or peritoneal dialysis)
- Kidney transplant recipients
- Unable to afford BP medications or lack transportation to clinic visits
- Hospice or nursing home care
- Dementia or cognitive impairment on the problem list

Sample Size

24 patients –We will randomize 12 patients into 2 groups

Interventions and Interactions

Pilot randomized controlled study.

Participants in the SMS intervention arm will receive usual care and SMS texting and phone calls. Study team members will send secure SMS messages to participants weekly for four weeks and then every other week until their next appointment.

The secure messaging system will be as follows

Introductory message:

Welcome to managing your blood pressure with the Nephrology/ Internal medicine clinics at Wake Forest. Try to take your BP meds at the same time every day to keep your BP under control! Make it part of your daily routine:

First week

Adherence checkpoint:

1. *Good morning! Did you take your blood pressure medications today?*

“No” Response:

1. *Let's try to stay on top of taking them daily! You can do this!*

Additional prompts:

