1. Screening: we will track the number of patients screened per month, the number enrolled per month, the proportion that are eligible who enroll.
2. Recruitment: number of participants who refuse to participate in the pilot at the time of recruitment and the reason why. Proportion of vulnerable patients screened but excluded because they did not own a phone with SMS capability.
3. Retention: the proportion of participants who continue to use the myHealth tool per month through three months will be tracked for the intervention.
4. Engagement: 12- SMS rate response of at least one home BP measurement. We will use 44% as our cut off based on an SMS study by Peters and colleagues²⁵.

Finally, we will monitor time needed for assessments and gather feedback on the participant burden.

B-Acceptability

Participants will complete the SUS in person on an I-Pad or over the phone. They will also be offered the opportunity to comment in their questionnaires about their experiences of taking part in the pilot. The SUS yields a single score on a scale of 0–100. A SUS score above a 68 would be considered above average. We will consider acceptable when >70 % of participants score the SUS above 68.²⁶

Secondary measures of interest

Medication adherence (MA) will be measured by administrating the four-item MAQ by the study coordinator during enrollment and at 3 months follow up visit. The MAQ was selected because it has been well-validated to identify adherence in HTN and scores have been shown to correlate well with a range of objective adherence measures.^{11,12}

SBP and DBP change at 3 months. BP will be measured during initial and follow up office visits by nurses or clinicians while patient is seated with automated arm devices according to standard office procedures. We will extract from the electronic medical record, SBP and DBP at enrollment and at 12 weeks follow up. The average change will be calculated and reported in mmHg.

No-show rate at 3 months' follow-up (f/u) clinic visits. If participants fail to come to their f/u visits within 7 days of their scheduled follow-up appointment, they will be considered as "no-shows". Our current clinic no-show rate is 30%, therefore if the study participants no-show rate is less than 30% we will consider our tool a feasible intervention.

Analytical Plan

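### Acceptability and home-BP engagement each carry two different success figures, and the plan does not say which one governs

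*Combined protocol and SAP*

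**What the plan says.** All four figures are in the current text of the combined protocol and SAP.

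- **Acceptability, Specific Aims (second hypothesis):** "> 75% will be satisfied with the service (OK or above on the usability survey". No SUS value is given for OK.
- **Acceptability, Outcome Measure(s), B-Acceptability:** "We will consider acceptable when >70 % of participants score the SUS above 68". The same paragraph explains the score: "A SUS score above a 68 would be considered above average".
- **Engagement, Specific Aims (first hypothesis):** "over 50% of contacted patients will respond to SMS messages and over 50% will check HBPM".
- **Engagement, Outcome Measure(s), A- Feasibility, item 4:** the measure is "SMS rate response of at least one home BP measurement", followed by "We will use 44% as our cut off based on an SMS study".
- **Size of the SMS arm:** the Sample Size section gives 24 patients and says "We will randomize 12 patients into 2 groups", most naturally 12 per arm. Aim 2, however, describes a single cohort of 24 for the SMS intervention.
- **Analysis set:** the Analytical Plan restricts the primary analysis to subjects who sent at least one BP measurement.

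**The concern.** Feasibility and acceptability are the subjects of Aims 1 and 2, and the Specific Aims present the pilot as the source of preliminary data for a later efficacy trial. With two success figures per outcome, a report could find its own hypothesis unsupported and still declare the outcome rule met, or the reverse.

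The choice between figures would not necessarily be made blind to results. Under Interventions and Interactions, the team tracks satisfaction surveys monthly and circulates monthly performance reports. A rule settled late could therefore be settled with the data in view, whatever the intention.

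**Working it through.** The plan gives no sample-size or power calculation, so there is no figure of its own to reproduce. The check asks which counts satisfy one rule and miss the other, and how likely those counts are.

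**Inputs.** Proportions >75% and >50% (Specific Aims); >70% and 44% (Outcome Measure(s)); n = 12 in the SMS arm (Sample Size, read as 24 split equally). Assumptions: all 12 are assessed, and engagement is the share of participants with at least one home BP measurement.

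**Step 1: smallest passing count at n = 12.**

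| Rule | 12 × cut-off | Count needed |
|---|---|---|
| Acceptability >75% | 9.00, must be exceeded | 10 |
| Acceptability >70% | 8.40 | 9 |
| Engagement >50% | 6.00, must be exceeded | 7 |
| Engagement 44% | 5.28 | 6 |

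On the percentages alone, 9/12 = 75.0% and 6/12 = 50.0% are the discordant counts. Each meets the Outcome Measure(s) figure and misses the hypothesis figure.

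**Step 2: chance of the discordant count.** P(X = r) = C(12, r) p^r (1 − p)^(12 − r), which is largest at p = r/12.

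- Acceptability at p = 0.75: 220 × 0.75^9 × 0.25^3 = 0.258.
- Engagement at p = 0.50: 924 × 0.5^12 = 924/4096 = 0.226.

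| Acceptability, true rate | Exactly 9 | At least 9 | At least 10 |
|---|---|---|---|
| 0.60 | 0.142 | 0.225 | 0.083 |
| 0.70 | 0.240 | 0.493 | 0.253 |
| 0.75 | 0.258 | 0.649 | 0.391 |
| 0.80 | 0.236 | 0.795 | 0.558 |

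| Engagement, true rate | Exactly 6 | At least 6 | At least 7 |
|---|---|---|---|
| 0.40 | 0.177 | 0.335 | 0.158 |
| 0.44 | 0.207 | 0.445 | 0.238 |
| 0.50 | 0.226 | 0.613 | 0.387 |
| 0.60 | 0.177 | 0.842 | 0.665 |

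Further out, exactly 9 has probability 220 × 0.9^9 × 0.1^3 = 0.085 at a true 90%. Exactly 6 has probability 924 × 0.3^6 × 0.7^6 = 0.079 at a true 30% or 70%.

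**Step 3: other denominators.** At n = 24 (Aim 2 wording), 17 or 18 is discordant for acceptability and 11 or 12 for engagement. With incomplete follow-up the conflict comes and goes:

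- Acceptability is discordant at n = 11 (8 passes), n = 8 (6) and n = 7 (5), but not at n = 10, 9 or 6.
- Engagement is discordant at n = 11 (5), 10 (5), 9 (4), 8 (4) and 6 (3), but not at n = 7.

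**Step 4: score definitions.** The steps above treat both acceptability rules as counting the same people as successes. They need not. One counts ratings of OK or better, the other SUS above 68. With no SUS value for OK, the resulting difference cannot be computed and could run in either direction.

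**Step 5: analysis set.** If engagement means at least one home BP measurement per participant, and it were computed on the Analytical Plan's primary set, numerator and denominator would be the same people. The rate would be 100% by construction.

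**The case against.** The best defence is that the two sections do different jobs. The Specific Aims label their figures hypotheses and call the first an estimate from a previous study. Only Outcome Measure(s) uses decision language. Expecting more than 75% while accepting more than 70%, or expecting over 50% with a floor of 44%, is coherent. This may well be the intended reading, but the plan does not state it, and it leaves the two acceptability score definitions unreconciled.

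The engagement pair is also less secure than the acceptability pair. The wording of item 4 is unclear and might describe a rate over messages or weeks rather than a share of participants. The 6/12 against 7/12 contrast holds only on the per-participant reading. That limits the arithmetic, but it also shows that the unit needs stating.

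The pilot is reported mainly with descriptive statistics and 95% intervals. Exact intervals are 43% to 95% for 9/12 and 21% to 79% for 6/12, so neither result statistically separates the competing cut-offs.

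A reader might infer three stronger things that the documents do not support:

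- **That these are go/no-go criteria for the efficacy application.** The plan promises preliminary data and does not make the application conditional on any threshold.
- **That Outcome Measure(s) always holds the easier rule.** Its proportions are lower, but if OK corresponds to a SUS value below 68, the hypothesis could be the easier acceptability rule.
- **That the rules would typically disagree about a quarter of the time.** Those probabilities are maxima, reached at true rates of 75% and 50%.

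**Conclusion.** The inconsistency is real and should be fixed. It is a matter of internal consistency in a 24-person pilot and does not touch the randomised comparison or safety. On percentages alone, with 12 SMS participants all assessed and engagement counted per participant, one count in each pair meets one figure and misses the other. The chance of that count is at most about 26% for acceptability (14% at a true 60%, 9% at 90%) and about 23% for engagement (8% at a true 30% or 70%). The acceptability conflict goes beyond the percentage, because the definition of a success differs too; the net direction of that difference cannot be determined from the plan.

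**What to change.** Before outcome data are reviewed, do one of the following:

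1. State one success rule per outcome, giving score definition, proportion, unit and denominator, in identical terms in Specific Aims and Outcome Measure(s); or
2. State explicitly that the Specific Aims figures are expectations and the Outcome Measure(s) figures are the decision rules.

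Under either option:

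- Define OK as a SUS value, or drop it.
- Say whether engagement is counted per participant or per message.
- Use all participants randomised to SMS as the engagement denominator, not the set with at least one BP measurement.
- Settle whether the SMS group is 12 or 24.

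The choice of figures belongs to the authors. The stricter stated proportions (at least 10/12 and at least 7/12) are one acceptable choice. Their cost is a lower chance of meeting the criterion: from 65% to 39% at a true acceptability of 75%, and from 61% to 39% at a true engagement of 50%. Pairing >75% with SUS above 68 would create a rule found in neither section, so it should be presented as a new decision. Otherwise the cost is a few sentences of protocol wording.

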Participants will be interviewed by the study team and those with a MAQ score of 1 to 4 will be classified as non-adherent will be invited to participate. The study team member will assess the potential participant's phone ownership, text messaging ability, text messaging willingness, and receptivity to the intervention (and record all this information). The MAQ cut-off was chosen for the study because it has been used in the literature in previous studies,²⁰⁻²² and the cut-off at this value provides a highly sensitive tool for identifying medication non-adherence.^{22,23}

Participants will be randomized into one of two groups: intervention SMS arm or the control arm. If enrolled in the intervention arm, the subjects will be contacted by phone via SMS and phone call. To ensure equal access to participation among women and minorities we will translate all materials and questions to Spanish. The privacy of potential subjects during recruitment will be protected by collecting only necessary identifiers and using a private room during the interview process.

As part of routine care, patients who present to the office with uncontrolled HTN receive instructions from their clinician on medication changes and are advised to return for a nurse visit in 2 weeks and a clinician visit in 3 months. During follow-up, the nurse checks the patient's blood pressure and contacts the clinician for further management if the BP is not controlled. Participants in the SMS arm will receive SMS messages to monitor their blood pressure in addition to this routine care whereas the control arm will only receive the standard provider education and monitoring for controlling blood pressure.

Baseline demographic characteristics of the participants will be collected. Participants will be followed with office (or phone if they no show for their visit) interviews at 2 weeks or 3 months to complete 2 validated scales: the MAQ, and SUS+ free comments

Study intervention participants will be provided with a blood pressure monitor to be used for measurement and extraction of HBPM information. Clinicians will be alerted through an in-basket message in the electronic medical record (Wake One) if the participants report BP outside the threshold range, and the patient will be sent an SMS and prompted to contact their clinic. The threshold range set for SBP is between 90 and 180 mm Hg and between 60 and 110 mm Hg for DBP for one-time measurements. These thresholds are made based on the

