potential subjects during recruitment will be protected by collecting only necessary identifiers and using a private room during the interview process.

Informed Consent

The study team will recruit patients in the renal and internal medicine clinics. Signed informed consent will be obtained from each subject. Participants will be consented in a private room in the clinic. Group assignment will be determined using blocked randomization.

Participants will either receive an educational pamphlet or use their own mobile phone to communicate with the study coordinator via SMS. HIPAA-compliant SMS text messages will be sent to participants through any of the local mobile phone network providers.

Confidentiality and Privacy

Confidentiality will be protected by collecting only information needed to assess study outcomes, minimizing to the fullest extent possible the collection of any information that could directly identify subjects, and maintaining all study information in a secure manner. To help ensure subject privacy and confidentiality, only a unique study identifier will appear on the data collection form. Any collected patient identifying information corresponding to the unique study identifier will be maintained on a linkage file, stored separately from the data. The linkage file will be kept secure, with access limited to designated study personnel. Following data collection subject identifying information will be destroyed after three years using a shredder, consistent with data validation and study design, producing an anonymous analytical data set. Data access will be limited to study staff. Data and records will be kept locked and secured, with any computer data password protected. No reference to any individual participant will appear in reports, presentations, or publications that may arise from the study. To prevent breach of confidentiality on subject's cell phone device the study team will ensure the subject is aware of the configuration feature on the device to only show text messages upon unlocking the phone.

Data and Safety Monitoring

The principal investigator will be responsible for the overall monitoring of the data and safety of study participants. The principal investigator will be assisted by other members of the study staff.

Reporting of Unanticipated Problems, Adverse Events or Deviations

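### The 3-month adherence questionnaire is given by the role that texts the SMS arm about pill-taking, so self-report pressure is likely to be greater in that arm than in controls

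*Combined protocol and SAP*

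**What the plan says.** Four parts of the combined protocol and SAP bear on this point.

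- **Who collects the outcome.** The section on secondary measures provides for "administrating the four-item MAQ by the study coordinator during enrollment and at 3 months follow up visit". The Design section adds: "Participants will be followed with office (or phone if they no show for their visit) interviews at 2 weeks or 3 months", and lists the MAQ among the scales completed there.
- **Who texts.** Informed Consent says that one group receives a pamphlet and the other will "use their own mobile phone to communicate with the study coordinator via SMS". Elsewhere the sender is described more broadly. Interventions and Interactions has "Study team members will send secure SMS messages to participants weekly for four weeks", and Design has "Text messages will be generated by Twilio platform".
- **What the texts say.** The adherence checkpoint under Interventions and Interactions opens with "Good morning! Did you take your blood pressure medications today". A yes brings praise and a thumbs-up emoji. A no brings encouragement and further prompts. An unfilled prescription or a side effect leads to a phone call and a message to the clinician. According to Design, controls receive usual provider education and monitoring only.
- **How the other scale is collected.** Under B-Acceptability: "Participants will complete the SUS in person on an I-Pad or over the phone". No device is named for the MAQ.

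The Background classes self-report and adherence scales as subjective and sets objective measures aside on grounds of cost and labour. The Analytical Plan compares adherence between arms by the Wilcoxon rank sum test, two-sided at 0.05, with Bonferroni-type adjustment. No section mentions a blinded or separate MAQ assessor.

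**The concern.** The MAQ is the trial's only measure of adherence, and there is no objective check on it. Over 12 weeks, SMS participants are asked about their pills, praised for one answer and followed up after the other. At 3 months they are asked about their pills again, by the role that the consent section gives as their texting contact. Controls meet the same interviewer without that history. An SMS participant therefore has more reason to give the approved answer.

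Randomisation balances who is asked. It does not balance what participants have learned about the expected reply. Neither the rank sum test nor a confidence interval can tell better pill-taking from better answers. The plan's support for the MAQ is that its scores correlate with objective measures, which does not address an interviewer linked to the intervention. Specific Aims says the pilot is to supply data for a later efficacy trial, so an inflated adherence difference could be carried into that trial's planning.

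**Working it through.** The plan gives no effect size, standard deviation or power for the MAQ, so there is no figure of its own to reproduce. The check has two parts.

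**1. The text**

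- Assessor at 3 months: study coordinator (Secondary measures of interest).
- Setting: interview, in the office or by phone (Design).
- Texting contact: study coordinator (Informed Consent), but also study team members (Interventions and Interactions) and a messaging platform (Design).
- Separation or blinding: none described.
- First MAQ: used to screen for eligibility (Design and Inclusion criteria), so it comes before randomisation and before any text. The differential problem therefore lies in the 3-month score.

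The same role is documented on both sides. The same individual is not.

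**2. What differential shading could do**

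Inputs from the plan: 24 participants, read as 12 per arm (Sample Size); four items scored 0-4, with higher scores meaning less adherent; two-sided Wilcoxon test.

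*Simple shift.* If k of 12 SMS participants each answer one item more favourably, the mean shift is k/12:

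- 2/12 = 0.17
- 4/12 = 0.33
- 6/12 = 0.50 points

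*Effect on the planned test.* The following are assumptions, not figures from the plan. There is no true effect. Each item is answered in the non-adherent direction with probability p = 0.4, 0.5 or 0.6. A share q of those answers in the SMS arm is reported as adherent. Control scores are then Binomial(4, p) and SMS scores Binomial(4, p(1 − q)), so the SMS mean falls by 4pq. With p = 0.5 and q = 0.2, the fall is 4 × 0.5 × 0.2 = 0.40 points. Each scenario was simulated 20,000 times with all 12 per arm assessed.

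The plan does not say how many tests share the Bonferroni-type adjustment. The last column assumes four secondary tests (MAQ, SBP, DBP, no-show): 0.05/4 = 0.0125.

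| Shading, SMS arm only | Mean shift (points) | False positives at 0.05 | False positives at 0.0125 |
|---|---|---|---|
| 0% | 0 | 0.043 to 0.046 | about 0.009 |
| 10% | 0.16 to 0.24 | 0.06 to 0.08 | 0.015 to 0.021 |
| 20% | 0.32 to 0.48 | 0.11 to 0.19 | 0.034 to 0.067 |
| 30% | 0.48 to 0.72 | 0.21 to 0.38 | 0.075 to 0.173 |

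If both arms shade, only the difference matters. With 10% in each arm, the rate at 0.05 stays at 0.042 to 0.047. With 10% in controls and 30% in the SMS arm, it is 0.12 to 0.19.

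**The case against.** A good deal can be said on the other side.

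- **Both arms are interviewed.** A reader might infer that socially desirable answering occurs in the SMS arm only. The documents do not support that. The coordinator gives the MAQ to everyone, and no-shows are telephoned about adherence barriers with no restriction by arm. The supportable claim is greater pressure in the SMS arm. This stands as a limit on the point.
- **The same person is not established.** A reader might infer that one individual texts and then assesses. Only the consent section names the coordinator as the texting contact; the other descriptions are wider. This also stands, but nothing in the plan keeps the two tasks apart.
- **Mode.** The plan does not say outright that the items are read aloud or kept off the device. It does say interview, and it names the I-Pad for the SUS alone.
- **The magnitudes are assumed, and the plan adjusts for multiplicity.** Both are true. Adjustment lowers the false-positive rates, but it leaves the shift in the estimate untouched. Nor is the 1-to-4 cut a 3-month endpoint: it defines eligibility, so crossing it should not be read as a planned result.
- **The outcome is secondary.** The pilot's aims are feasibility and acceptability, and none of their criteria uses the MAQ. The plan also acknowledges that self-report is subjective. This limits the importance of the point. It does not remove the flaw from a comparison that the plan intends to make.

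**Conclusion.** The concern holds in a limited form. The plan assigns the 3-month MAQ to a role that it also names as the SMS arm's texting contact, with no blinding or separation. The between-arm adherence comparison may therefore lean towards SMS with no change in pill-taking.

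The documents do not give the size of this lean. The shifts of 0.17 to 0.50 points and the simulated false-positive rates show what would follow if shading of the assumed amount occurred; they do not estimate it. The conclusion rests on two judgements: that prior prompting and praise raise the pressure to report well, and that nothing outside the documents already separates the tasks.

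A reader might go further and infer that an adherence difference from this pilot would be worthless, or that the pilot's main aims are compromised. Neither follows. The issue affects how one secondary comparison is read and carried forward. It deserves correction because the correction is cheap and has to be made before the data are collected.

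**What to change.** Amend Secondary measures of interest as follows:

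1. Participants in both arms complete the 3-month MAQ themselves on the I-Pad already named for the SUS, before any discussion of adherence at that visit.
2. The enrollment MAQ may stay as the screening interview, provided its mode is the same in both arms.
3. Where a participant needs reading help or a phone interview, the items are asked, where available, by an existing team member who has not texted or called that participant.
4. The mode and the asker are recorded for every MAQ.
5. The limitations state that participants know their arm and that self-report remains unblinded, so differential reporting is reduced but not removed.

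The cost is one more four-item form on a device already in use, two recorded fields and a few sentences. The plan does not give the team's size, so an uninvolved asker cannot be guaranteed. Low education is one route to eligibility and no-shows are interviewed by phone, so some participants will still have the items read to them. Modes will then be mixed at follow-up, and can differ from enrollment, which is why the mode must be recorded and reported by arm.
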